PATCH 3 Inclusion (Sub-Study 2): Currently employed as a health care worker ([name]; Doctor of Osteopathic Medicine, DO; Nurse Practitioner, NP; Physician's Assistant, PA; and [name] or other members of the medical care team with significant COVID-19 exposure); asymptomatic and presumed negative for COVID-19 (no confirmatory testing conducted); scheduled for an average of ≥ 20 hours per week of clinical care over the next two months (or equivalent indicating at least part-time employment). Participant will be asked to comply with their employer's potential or confirmed COVID-19 incident protocol and must agree to undergo COVID-19 testing per standard of care using an FDA approved method upon the presentation of symptoms indicative of an influenza like illness; if a confirmatory COVID-19 diagnosis is given, participant will be offered to cross-over to HCQ 600 mg qd for 14 days. At the end of the 60-day medication period, participants remaining undiagnosed for COVID-19 will undergo virus and serology testing. (See Appendix- PATCH3 process flows)

PATCH 2 & PATCH 3 Combined Exclusion Criteria

(See Study Exclusions and Content Job Aid)

- Allergy to hydroxychloroquine, 4 aminoquinolines, or quinine
- Known G6PD deficiency
- Pregnant or lactating or intention of becoming pregnant during the study as self-reported during enrollment screening
- Receiving any trial treatment drug for 2019-nCoV within 14 days prior to screening evaluation (off label, compassionate use or trial related)
- Known retinal disease including but not limited to macular degeneration, retinal vein occlusion, visual field defect, diabetic retinopathy
- History of interstitial lung disease severe emphysema or asthma, or chronic pneumonitis Current diagnosis of porphyria or psoriasis
- Serious intercurrent illness that requires active intravenous therapy, intense monitoring, or frequent dose adjustments for medication including but not limited to infectious disease, cancer, autoimmune disease, cardiovascular disease

PATCH 2 & 3 TRIAL

- Have undergone major abdominal, thoracic, spine or CNS surgery in the last two months, or plan to undergo surgery during study participation
- Is receiving cytochrome P450 enzyme-inducing anticonvulsant drugs (i.e. phenytoin, carbamazepine, Phenobarbital, primidone or oxcarbazepine) within four weeks of the start of the study treatment
- Currently taking digoxin
- History or evidence of increased cardiovascular risk including any of the following:

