5. Package containing blinded study drug supply, study journals (medicine log, symptom tracker and experience log) and study documents (details on aims, design, consent forms, and any additional instructions) are delivered to the address provided by participant as place of residence during study. Delivery of blind study drug supply will occur in two shipments, each containing a 30-day supply. Day 1 is defined as the first day the blinded study drug is taken by the participant.
6. Each day active medication is taken (HCQ or placebo), participants will record 1) temperature (to be reported twice daily, either via thermometer or self-report); 2) time medication taken; and 3) any symptoms and AEs.
7. Every week, clinical research coordinators will review the study portal to assess for AEs and indication of reported symptoms indicative of influenza like illness. The research coordinator will also review self-reported fever and/or temperature. If COVID-19 symptoms are evident, the research coordinator will outreach to the HCW (at clinic or by phone). Clinical research coordinators may clinically escalate any medical determinations to Co-PI following study portal review.
8. The HCW also has access to the study coordinators via the study phone number. If the HCW feels symptomatic, then he/she should call the clinical research coordinator team, and document symptoms in the study portal. Clinical research coordinators may clinically escalate any medical determinations to Co-PI.
9. If during the study symptoms indicative of an influenza like illness present, participant will be asked to comply with their employer's potential or confirmed COVID-19 incident protocol and be tested for COVID-19 by an accepted method. Participants negative for COVID-19 continue with the assigned blinded study drug regimen.
10. If confirmed COVID-19 diagnosis, participant will be unblinded. Participants assigned to HCQ can continue with medication schedule. Individuals assigned to the placebo arm will be offered the opportunity to cross-over to HCQ 600 mg daily for 14 days. Individuals will be expected to continue self-reporting temperature, time medication taken and any symptoms/AEs into the study portal while taking active HCQ medication.
11. Participants who remain undiagnosed for COVID-19 by the end of the medication period (Day 60) will be asked to undergo COVID-19 and serology testing for IgM/IgG on either Day 61, 62, or 63.

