3. Immunosuppressive medications, including, corticosteroids at doses exceeding 10mg/day of prednisone or equivalent, methotrexate, azathioprine, and TNF-alpha blockers. Use of immunosuppressive medication for the management of study treatment-related AEs or in subjects with contrast allergies is acceptable. In addition, use of topical, inhaled and intranasal corticosteroids is permitted
4. Live attenuated vaccines during the study through 180 days after the last dose of both drugs

7.3 Duration of Protocol Treatment and Follow-up.

PATCH 2 (Sub-Study 1) duration of treatment is 14 days (two weeks) with follow-up with COVID-19 testing on Day 15, 16 or 17, and Day 29, 30 or 31 where Day 1 marks the first day blinded study drug is taken by the participant.

PATCH 3 (Sub-Study 2) duration of treatment is up to 60 days with an option to cross-over for participants taking placebo upon presentation of symptoms indicative of an influenza like illness and testing positive for COVID-19 (or a COVID-19 diagnosis is made by a health care provider). Participants remaining undiagnosed for COVID-19 by Day 60 will undergo testing for SARS-CoV-2 and IgM/IgG antibodies on either Day 61, 62, or 63. The maximum study medication duration and follow-up testing is 63 days.

7.4 Crossover from Control to HCQ arm.

PATCH 2 (Sub-Study 1): There is no cross-over.

PATCH 3 (Sub-Study 2): Participants that develop symptoms indicative of an influenza like illness and diagnosed with COVID-19 will be unblinded. If they were assigned to the placebo arm and deemed appropriate, they will be offered the option crossover to HCQ 600 mg qd for 14 days.

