	
 The HCQ Medication Guide opens with: “You have received your medication tablets in this box. These tablets may be a placebo or they may be the active hydroxychloroquine (HCQ) medication. Below is a list of possible side effects from taking active HCQ.”

PATCH3 HEALTH CARE WORKER CROSSOVER KIT

Content	Description
	
CROSSOVER MEDICATION Unblinded Active HCQ - 42 tabs Medication ID: [bottle serial number] Contents: 42 tablets Directions: Take 3 pills in the AM daily for 14 days. No refill. Store at [insert storage instructions from the manufacturer] Caution: New Drug - Limited by Federal (or United States) law to investigational use

	
CROSSOVER GUIDE This guide is to support the health care worker with instructions when crossing over from placebo to HCQ should they qualify.

E FREQUENTLY ASKED QUESTIONS (FAQ)

Type of Question	Question	Response
Study Info	What is the PATCH Study?	PATCH, also known as Prevention and Treatment of COVID-19 with Hydroxychloroquine (HCQ), is a research study that is being conducted by ProHEALTH NY, University of Pennsylvania, and UnitedHealth Group Research & Development to determine if HCQ can be an effective antiviral medication for preventing and treating COVID-19.
Study Info	What will be expected of me if I decide to participate in this study?	A package will be sent to you with either HCQ active or placebo pills. We ask that you take your medication according to the package direction, check your temperature twice daily or report symptoms of fever, record and report any adverse events, and upload this information daily through the study portal at patchstudy.com for the full duration of this study. You'll also be asked to get your swab samples taken at the end of the study.
Study Info	Can anyone join?	The PATCH2 Study is focused on recruiting patients who are: 
 • between the ages of 50-75 years of age • experiencing COVID-19 symptoms such as cough, fever, and/or sore throat • being sent home for a 14-day self-quarantine after being tested for COVID-19

PATCH 2 & 3 TRIAL

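### The 63-day maximum for PATCH 3 in Section 7.3 cannot hold a 14-day crossover course that starts on Day 51 or later

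*Combined protocol and SAP*

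**What the plan says.** Section 7.3 opens its PATCH 3 paragraph with the treatment period and the crossover together: "PATCH 3 (Sub-Study 2) duration of treatment is up to 60 days with an option to cross-over for participants taking placebo". It then sets the final tests: "Participants remaining undiagnosed for COVID-19 by Day 60 will undergo testing for SARS-CoV-2 and IgM/IgG antibodies on either Day 61, 62, or 63". It closes with the cap: "The maximum study medication duration and follow-up testing is 63 days". The cap carries no exception.

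The crossover course is 14 days wherever it is described:

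- Section 4.0, PATCH 3 item 10: "Individuals assigned to the placebo arm will be offered the opportunity to cross-over to HCQ 600 mg daily for 14 days". The same item says of the other arm: "Participants assigned to HCQ can continue with medication schedule".
- Section 6.0 gives the placebo arm an optional 14-day crossover after symptoms and a confirmed diagnosis.
- Section 7.4, for placebo participants deemed appropriate: "they will be offered the option crossover to HCQ 600 mg qd for 14 days".
- Appendix 4, crossover kit of 42 tablets: "Take 3 pills in the AM daily for 14 days. No refill".

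None of these gives a latest day for starting the course, shortens a late course, or says that crossover drug falls outside the 63 days.

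**The concern.** A 14-day course that can follow a diagnosis on any day up to Day 60 does not fit under a 63-day maximum. For a late diagnosis, study staff could read the text in three ways: crossover is refused, the course is cut short, or it runs past the stated maximum. The protocol should not leave that open for participants who start unblinded drug during acute COVID-19.

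The trigger is also described inconsistently. Item 10 asks only for a confirmed diagnosis. Sections 6.0, 7.3 and 7.4 also require symptoms of an influenza-like illness. It is therefore unclear whether a positive end-of-study test on Day 61-63 could start a course.

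A related but separate matter is how long participants are observed for the PATCH 3 secondary summaries of adverse events and hospitalisation, since neither has a common window.

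**Working it through.** **Inputs from the plan**

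- Stated maximum: 63 days (7.3).
- Blinded drug: up to 60 days (6.0, 7.3). Supply agrees: 2 bottles x 90 tablets / 3 per day = 60 days (Appendix 4).
- Final testing of undiagnosed participants: Day 61, 62 or 63 (7.3; 4.0 PATCH 3 item 11).
- Crossover: 14 days (4.0 item 10, 6.0, 7.4). Supply agrees: 42 / 3 = 14 days (Appendix 4).
- Day 1 is the first day of blinded drug (4.0 PATCH 3 item 5).
- Placebo infection rate 10%, 175 per arm (16.1).

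**Assumptions, used only for size:** every expected placebo infection is diagnosed during Days 1-60, uniformly over those days; all of these participants cross over and complete the course; the lag L from diagnosis to first crossover dose is 0-3 days.

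**1. The plan's figure.** 60 + 3 = 63. It reproduces exactly for a participant who never crosses over.

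**2. The crossover course.** With start day s counted as the first of 14 dosing days, the last dose is on day s + 13. Requiring s + 13 ≤ 63 gives s ≤ 50. A start on Day 51 ends on Day 64; a start on Day 60 ends on Day 73, 10 days over. Reading the cap as days on medication changes nothing: (s - 1) days of placebo + 14 of HCQ = s + 13.

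**3. Number and length of overruns.** For diagnosis on day d, s = d + L. The course overruns when d + L > 50, which covers 10 + L of the 60 diagnosis days. The overrun is d + L - 50 days, so it runs from 1 to 10 + L with mean (11 + L)/2. Expected placebo infections are 0.10 x 175 = 17.5, and the number affected is 17.5 x (10 + L)/60.

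| Lag L | Diagnosis days affected | Share | Participants | Overrun (days) | Mean overrun |
|---|---|---|---|---|---|
| 0 | 51-60 (10) | 16.7% | 2.9 | 1-10 | 5.5 |
| 1 | 50-60 (11) | 18.3% | 3.2 | 1-11 | 6.0 |
| 2 | 49-60 (12) | 20.0% | 3.5 | 1-12 | 6.5 |
| 3 | 48-60 (13) | 21.7% | 3.8 | 1-13 | 7.0 |

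**4. Positives at final testing.** If they qualify, same-day starts on Day 61, 62 or 63 end on Day 74, 75 or 76.

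**5. Observation time by arm.** Section 9.2 ends adverse event reporting at the last dose. Compare two participants diagnosed on the same day, with same-day crossover in the placebo arm and an HCQ participant who completes 60 days. Diagnosis on Day 20: reporting ends on Day 33 for the crossover and Day 60 for HCQ. Diagnosis on Day 60: Day 73 and Day 60. The two are equal for a start on Day 47 (47 + 13 = 60). The difference changes sign and arises whatever the cap is.

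**The case against.** The best defence is that the cap directly follows the sentence on testing undiagnosed participants, so 63 days may describe only the path without crossover. That reading is possible. But the sentence claims a maximum for study medication, has no exception, and stands in the paragraph that introduces crossover, so the text does not settle it. The crossover flow figure and the crossover guide are not readable here. A latest start day may be given there, and its absence can be claimed only for the readable text.

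Five stronger readings are tempting, and the documents do not support them:

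- *Late crossovers take drug after the study has ended.* Section 7.3 caps medication and follow-up testing; it does not declare a study end at Day 63.
- *Adverse events on late crossover drug go unreported.* Section 9.2 runs reporting to the last administration, item 10 expects self-reporting while HCQ is taken, Section 9.3 follows unresolved events, and Section 10.0 collects serious events from consent.
- *The 63-day figure makes the arms' observation windows differ.* Step 5 shows that the crossover design does this, for early diagnoses as well as late ones.
- *HCQ participants may also be owed 14 further days*, because Section 3.1 says "if a confirmatory COVID-19 diagnosis is given, participant will be offered to cross-over to HCQ 600 mg qd for 14 days" without naming an arm. The synopsis dosing entry, item 10 and Sections 6.0, 7.3 and 7.4 all tie crossover to placebo.
- *Each affected participant overruns by 10-13 days.* That is the worst case, for a Day 60 diagnosis only.

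On Day 61-63 positives, the order of the items in Section 4.0 favours the narrow reading: item 10 follows the symptom-triggered test in item 9, and final testing comes afterwards in item 11. The plan does not say so outright.

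**Conclusion.** The inconsistency is real and minor. The 63-day maximum in Section 7.3 and a full 14-day crossover cannot both hold for any start from Day 51 on. At most about 3-4 placebo participants would be affected. This is an upper bound: crossover is optional and subject to being deemed appropriate, and some of the 10% may be found only at Day 61-63 testing. A rise or fall in incidence over the 60 days would change the share falling late.

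The primary endpoint is reached at diagnosis, before any crossover dose, so the primary comparison, power and alpha do not depend on this. Section 16.2 plans no significance tests for secondary endpoints. The documents do not show whether the cap or the crossover rule should give way, and nothing here favours either.

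The separate gap concerns the secondary summaries. Section 15.2 gives a 30-day hospitalisation window for PATCH 2 and none for PATCH 3. Section 16.2 compares adverse event counts per participant between groups, while the reporting period varies with arm and date of diagnosis.

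**What to change.** Reconcile the 63-day maximum in Section 7.3 with Section 4.0 item 10, Sections 6.0 and 7.4 and the crossover kit, so that one rule and one matching maximum apply throughout. Say explicitly whether a positive Day 61-63 test can trigger crossover. Which rule governs is for the sponsor to decide.

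Separately, in Sections 15.2 and 16.2, state one common window, counted from Day 1 or randomisation, for the between-arm adverse event and hospitalisation summaries, and report events on crossover HCQ separately.

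The reconciliation costs wording, plus, if late courses are to be completed, a few extra days of portal follow-up for a few participants. The common window means collecting events from participants whose last dose falls before its end. A window that ends within the 63 days already planned keeps this small, whereas one long enough to cover late crossover courses would extend follow-up for all 350.

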8.0 TOXICITY CRITERIA, MONITORING, DOSE DELAYS AND MODIFICATIONS

8.1 Toxicity Criteria

This study will utilize the DAIDS table for grading adult adverse events (AEs). A copy of the DAIDS grading system is available at: <https://rsc.niaid.nih.gov/sites/default/files/daidsgradingcorrectedv21.pdf>. All appropriate treatment areas should have access to a copy of the DAIDS grading table.

8.2 Dose Delays

Major Events are Grade 3 and 4 hematologic and non-hematologic toxicities that are not treatment related. Treatment should be delayed for major events if HCQ may further complicate the non-treatment related event. If a major event requires a delay of treatment, treatment must be delayed until toxicity is resolved (\leq Grade 2 or \leq Baseline). For treatment-related toxicities and major events, if toxicity is not resolved in ≤ 7 days, participant will be taken off treatment unless there is an exception granted by the medical monitor.

8.3 Ocular toxicity

The only toxicity that requires discontinuation of HCQ is retinopathy. Published literature indicates HCQ retinopathy is idiosyncratic and is uncommon in patients receiving HCQ for less than a few years. Our ongoing study of dabrafenib, trametinib, and HCQ (BAMM; NCTNCT02257424) found no clinically meaningful ocular toxicity in 10 patients studied extensively with serial ocular exams (21). Therefore, we have not included mandatory ocular exams in this protocol. However, if there is a visual field deficit, retinal vein occlusion, serous retinopathy, bullseye retinopathy, or retinal detachment, HCQ should be permanently discontinued.

8.4 Participant Safety Monitoring and Data Collection

Adverse events will be captured via self-report by participants within the study portal. Participants are instructed to contact the study team at the phone number provided in the Welcome Packet to report all adverse events. The study team will reach out to the participant to gather additional information surrounding the adverse event in order to complete DAIDS grading if necessary. Additional information pertaining to the adverse event will be captured within the study portal by the study team and reviewed by the PI's for causality to study drug. Adverse events meeting seriousness criteria will be reported to the IRB as noted below.

PATCH 2 (Sub-Study 1):

Clinical Symptom Monitoring: Participants will be contacted three times per week to assess AEs and COVID-19 symptoms and collect/review self-reported AE's. Worsening COVID symptoms and/or new or worsening AE's will be reviewed by the PI's for causality to study drug.

Temperature Measurements: Home quarantined participants will be asked to report twice daily either presence of fever or temperature and record the measurements.

COVID-19/SARS-CoV-2 Testing: On Days 15-17 and 29-31, participants will undergo follow-up testing for COVID-19.

Pill Count and Journal: Participants will be contacted three times per week and following the end of treatment to compare data entry on the portal and collect any missed entries over the phone.

Monitoring Co-Inhabitants: Participants will be contacted three times per week to identify if any co-inhabitants have developed symptoms and/or tested positive for COVID-19. Participants will also be asked to provide a description of co-inhabitants' symptomology, and time of positive testing for COVID-19 via self-reporting.

PATCH 3 (Sub-Study 2):

Adverse events will be captured solely based on participant self-reporting via the study portal and/or by calling the study team at the number provided in the Welcome Packet. The study team will review the portal for self-reported AE's not previously reported to the study team. New AEs not previously reviewed which cannot be

PATCH 2 & 3 TRIAL

graded based upon self-reported data within the portal will require follow-up from the study team to gather additional information from the participant. New or worsening AE's will be reviewed by the PI's for causality to study drug.

COVID-19/SARS-CoV-2 testing: Upon the presentation of symptoms indicative of an influenza like illness, participants will be asked to undergo testing for SARS-CoV-2 virus. Participants undiagnosed for COVID-19 at Day 60 will also be tested for SARS-CoV-2 and IgM/IgG antibodies (via serology testing) on either Day 61, 62, or 63.

Clinical Symptom monitoring: The study team will assess AEs, symptoms, and record temperature (either reported temperature or self-report of fever) for any participants taking active medication (placebo or HCQ). Worsening COVID symptoms and/or new or worsening AE's will be reviewed by the PI's for causality to study drug. The rate of conversion to receiving a positive COVID-19 test result in each arm at the 2-month mark will be used to assess the primary endpoint.

Pill count and Journal: Participants will be contacted to compare data entry on the portal and collect any missed entries over the phone.

Participants will be instructed to call 911 upon immediate presentation of the following symptoms as identified by the CDC as requiring emergency action: bluish lips or face; new confusion/dizziness or inability to arouse; persistent pain or pressure in the chest (not caused by coughing); and difficulty breathing (including severe shortness of breath and single word speech).

Participant confidentiality is strictly held in trust by all personnel granted access to the trial data. Therefore, the study data, and all other information generated will be held in strict confidence. No information concerning the study, or the data will be released to unauthorized parties.

The study investigators and study team, the research sponsor and its designees, personnel from ProHealth with authorized access to study data, government agencies, reviewing Institutional Review Board (IRB), regulatory agencies and/or company supplying study product may inspect all documents and records required to be maintained by the sponsor, including but not limited to, clinical, pharmacy and lab records for participants enrolled in the study. All applicable parties will permit access to such records.

The participant's study contact information will be securely stored within the online study portal for internal use during the study. At the end of the study, all records will continue to be kept in a secure location for as long as dictated by the reviewing IRB and institutional policies.

Study participant research data, which is for purposes of statistical analysis and scientific reporting, will be transmitted to and stored at UHG R&D in a de-identified manner. This will not include participant's contact or identifying information, unless otherwise specified in the informed consent form. Rather, individual participants and their research data will be identified by a unique study identification number. The study data entry and study management systems will be secured, and password protected. At the end of the study, study data will be de-identified and may be made public.

UHG R&D follows the standards of HITRUST for data management and data governance. Our data always remains encrypted in transit and at rest. Our data has managed access with expiration dates, and we follow minimum use guidelines with regard to dataset usage. UHG R&D uses Google Cloud Platform (GCP) for the storage of all encrypted data. UHG R&D has a dedicated Data Integration team for data management and data governance objectives and this team serves as the "Gate Keeper" of identifiable data. UHG R&D utilizes a "Clean Room" for data acquisition and isolation of identifiable data. The Clean Room is an environment that requires elevated access permission by a separate set of credentials. Access is limited to a small scope of approved "white

PATCH 2 & 3 TRIAL

listed" locations and to specific individuals filling a specific list of objectives associated with the Data Services department at UHG R&D.

